**CONFIDENTIAL**

204837

Laboratory Assessments	Parameters		
Hematology	Platelet count	RBC indices:	Leukocyte (white blood cell) count with Differential
	Erythrocyte (red blood cell) count	Mean corpuscular volume (MCV)	Neutrophils (absolute and segmented)
	Hemoglobin	Mean corpuscular hemoglobin (MCH)	Lymphocytes
	Hematocrit	Mean corpuscular hemoglobin concentration (MCHC)	Monocytes
	Reticulocyte count	Erythrocytes (red cell) distribution width (RDW)	Eosinophils
			Basophils
Clinical Chemistry	Potassium (serum)	Aspartate aminotransferase (AST)	Albumin
	Calcium (albumin-corrected)	Alanine aminotransferase (ALT)	Blood Urea Nitrogen (BUN)
	Phosphate	Bilirubin (total, direct and indirect)	
Iron parameters	Iron (serum)	Ferritin	UIBC
	Hepcidin	TIBC	TSAT
Lipid parameters	Total cholesterol	LDL-C (direct)	HDL-C
Other laboratory tests	Serum pregnancy test	High-sensitivity C-reactive protein (hsCRP)	HemoCue Hgb
	Estradiol	Intact parathyroid hormone (iPTH)	Stored sample (blood)
	FSH	Erythropoietin (EPO)	
	Hemoglobin A1c (HbA1c)	Vascular Endothelial Growth Factor (VEGF)	

MCV, mean corpuscular volume; MCH, mean corpuscular hemoglobin; MCHC, mean corpuscular hemoglobin concentration; RDW, red blood cell distribution width; AST, aspartate transaminase; ALT, alanine transaminase; UIBC, unbound iron binding capacity; TIBC, total iron binding capacity; TSAT, transferrin saturation; LDL-C, low density lipoprotein-C; HDL-C, high density lipoprotein-C;

Summaries of central laboratory Hgb values, HemoCue Hgb values, iron parameter values (serum iron, ferritin, hepcidin, TIBC, TSAT, UIBC), PD parameters (EPO, VEGF), and lipid parameter values (total cholesterol, direct LDL-C, HDL-C) are included in the separate efficacy, safety, and pharmacodynamic sections and will not be included with clinical laboratory displays. However, these parameters may be included in PCI summaries.

The clinical chemistry tests performed in this study include ALT, AST and bilirubin. In addition to being summarized with the clinical chemistry values, these laboratory values will be included in some of the Hepatobiliary (liver) displays.

In addition to the visits listed for the laboratory assessments in the Schedule of Activities table (see Section 14.2.1), any of these assessments may be performed at an unscheduled/retest visit at the discretion of the investigator. See Section 14.5.2 for handling of unscheduled values. The laboratory's normal range values will be provided by the central laboratory, and potential clinical importance thresholds are defined in Section 14.8.1.

All of the tabular summaries described below will include summaries in SI units; conventional units will also be provided for the following laboratory tests: MCHC, total calcium, albumin-corrected calcium, phosphate, albumin, BUN, total cholesterol, LDL-C, and HDL-C. Conversions from SI units to conventional units are included in Section 14.6.4. Hemoglobin summaries will only use conventional mg/dL units. Summaries of reticulocytes will be provided for the total count and percent of total erythrocytes and summaries of neutrophils, lymphocytes, monocytes, eosinophils, and basophils will be provided for total counts and differentials (percent of total leukocytes). TSAT will be reported in the conventional unit (%).

The clinical laboratory safety analyses will be based on the Safety population, unless otherwise specified.

#### **8.4.1. Planned Clinical Laboratory Safety Displays**

##### *Clinical Chemistry*

Continuous on-treatment values (see Section 14.4.1) will be summarized using mean, standard deviation, minimum, P25, median, P75, and maximum for each scheduled visit and for baseline and end of treatment (see Section 14.6.4) by treatment group.

Continuous on-treatment change from baseline values will be summarized using mean, standard deviation, minimum, P25, median, P75, and maximum for each scheduled visit and for end of treatment (see Section 14.6.4) by treatment group.

The number and percentage of subjects with on-treatment worst case laboratory results relative to the normal range which are post-baseline relative to baseline will be summarized by laboratory test, category, and treatment group. See Section 14.6.4 for additional information on worst case values and normal range categories.

The number and percentage of subjects with on-treatment worst case laboratory results relative to PCI criteria (see Section 14.8.1) which are post-baseline relative to baseline will be summarized by laboratory test, category, and treatment group. See Section 14.6.4 for additional information on worst case values and PCI categories.

##### *Hematology*

The displays presented for clinical chemistry laboratory values will also be presented for the hematology central laboratory tests listed in Section 8.4.

### *Other Laboratory Tests*

The displays presented for clinical chemistry laboratory values will also be presented for the other laboratory tests listed in Section 8.4.

The number and percentage of subjects with on-treatment worst case iron parameter results relative to PCI criteria (see Section 14.8.1) which are post-baseline relative to baseline will be summarized separately by laboratory test, category, and treatment group. See Section 14.6.4 for additional information on worst case values, normal range categories and PCI categories.

On-treatment hsCRP values will be log-transformed (see Section 5.2.2) and summarized using geometric mean, coefficient of variation, minimum, P25, median, P75, and maximum for each scheduled visit by treatment group.

Percent change from baseline in log-transformed (see Section 5.2.2) on-treatment hsCRP values will be summarized using geometric mean, 95% confidence interval, minimum, P25, median, P75, and maximum for each scheduled visit by treatment group.

### *Hepatobiliary (Liver)*

Please refer to the protocol for details of liver chemistry increased monitoring and stopping criteria.

Liver monitoring/stopping events will be summarized by treatment group.

Hepatobiliary laboratory abnormalities will be summarized by treatment group.

Medical conditions for subjects with liver stopping events and substance use for subjects with liver stopping events will be listed.

A scatter plot of maximum on-treatment ALT values versus baseline ALT values will be produced.

A scatter plot of maximum on-treatment total bilirubin (xULN) versus maximum on-treatment ALT (xULN) values will be produced.

### *All Laboratory*

A listing of all chemistry data, a listing of all hematology data, and a listing of all other laboratory data will be provided.

In addition, for subjects with abnormalities of potential concern, a listing of all chemistry data, a listing of all hematology data, and a listing of all other laboratory data will be generated separately.

A listing of laboratory data with character results will be provided.

## 8.5. Other Safety Analyses

The analyses of non-laboratory safety test results including ECGs and vital signs will be based on GSK Core Data Standards, unless otherwise specified. The details of the planned displays are presented in [Appendix 10: List of Data Displays](#).

### 8.5.1. Electrocardiograms

A summary of the number and percentage of subjects who had normal, abnormal and/or clinically significant ECG findings will be displayed by treatment group. For all ECG parameters, change from baseline in ECG values at week 52 will be summarized by treatment group.

The number of subjects with maximum QTc values (i.e., worst case) post-baseline relative to baseline will be summarized by test (e.g., QTcB Interval, Aggregate) and category for each treatment group.

Subjects will also be summarized by a categorization of their maximum increase in QTc value (e.g., QTcB Interval, Aggregate) (i.e., worst case) post-baseline relative to baseline.

### 8.5.2. Vital Signs

Vital signs are assessed in this study according to the schedule outlined in the Schedule of Activities table (see Section [14.2.1](#)) and include the following assessments:

- HR (pre- and post-dialysis)
- Weight (pre- and post-dialysis)
- Estimated Dry Weight (EDW, recorded in the eCRF only at Day 1, full study visits, and Week 52)

Summaries and analyses of BP values are described in earlier safety sections and will not be included with vital signs summaries. However, BP values will be included in PCI summaries.

The vital signs analyses will be based on the Safety population, unless otherwise specified.

Vital sign values will be summarized using mean, standard deviation, minimum, P25, median, P75, and maximum for each scheduled visit and for baseline and end of treatment by treatment group. Separate summaries for HR and weight measured pre- and post-dialysis will be provided.

Vital sign change from baseline values will be summarized using mean, standard deviation, minimum, P25, median, P75, and maximum for each scheduled visit and for end of treatment by treatment group. Separate summaries for HR and weight measured pre- and post-dialysis will be provided.

**CONFIDENTIAL**

204837

The number and percentage of subjects with on-treatment or post-treatment worst case vital sign results relative to PCI criteria (see Section 14.8.3) which are post-baseline relative to baseline will be summarized by test, category, and treatment group. See Section 14.6.4 for additional information on worst case values and PCI categories. Post-dialysis BP values and heart rate outside of the PCI range will be summarized separately.

The difference between on-treatment post-dialysis weight and estimated dry weight will be summarized using mean, standard deviation, minimum, P25, median, P75, and maximum for each scheduled visit and for baseline and end of treatment by treatment group. A corresponding line plot will be provided to display this data graphically.

A listing of all vital signs data for subjects with post-dialysis vital signs values outside of PCI criteria will be provided.

**8.5.3. Pregnancy**

A listing of all subjects who became pregnant during the study will be included.

**8.5.4. COVID-19 Analyses**

The following COVID-19 related displays will be provided.

A summary of the number and percentage of subjects for the following assessments will be produced: Case Diagnosis, COVID-19 Test performed, and Results of the COVID-19 test.

A summary of exposure adjusted incidence rates over time (see Section 14.6.4) will be produced by treatment group for any AE, any SAE, and any Severe AE, for two periods – pre COVID-19 pandemic and during COVID-19 pandemic. The summary will be produced overall, by Country, Region, Sex, and by Age at randomization (Grouping 2) (see Section 5.4.2). A summary of exposure adjusted incidence rates by treatment group will also be produced for Common (>5%) AEs for two periods – pre COVID-19 pandemic and during COVID-19 pandemic.

## 9. PATIENT REPORTED OUTCOMES ANALYSIS

This study includes the following patient reported outcomes (PROs) that are assessed according to the schedule in the Schedule of Activities table in Section 14.2.1:

- Patient Global Impression of Severity (PGI-S)
- Patient Global Impression of Change (PGI-C)

Additional details on these questionnaires can be found in Section 14.6.7.

Except for baseline, only on-treatment post-baseline PGI-S and PGI-C will be summarized/analyzed, unless otherwise specified.

Patient Reported Outcomes Statistical Analyses: Symptom Severity & Change
Secondary Endpoint(s)

 
• Change from Baseline at Wk 8, 12, 28, 52 in PGI-S
 

Exploratory Endpoint(s)

 
• Shift tables (Baseline to Weeks 8, 12, 28, and 52) in PGI-S
 
• N (%) of patients within each PGI-C symptom change level at Weeks 8, 12, 28, 52
 

Model Specification

 
• Scoring for the PGI-S and PGI-C parameters is outlined in Section 14.6.7.
 
• The mean change from baseline in PGI-S score will be analyzed using an MMRM approach with an unstructured covariance matrix to compare the difference in means between arms. The models will be fitted to data collected after baseline up to Week 52. The model will include factors for treatment, time, region, baseline PGI-S score value and the baseline PGI-S score by time and treatment by time interaction terms. Analyses will be done with the MIXED procedure in SAS, using the Kenward-Roger option to estimate denominator degrees of freedom and standard errors.
 

Model Results Presentation

 
• PGI-S scores will be summarized using mean, standard deviation, minimum, P25, median, P75, and maximum by treatment group at all scheduled visits.
 
• Change from baseline in PGI-S values will be summarized using mean, standard deviation, minimum, P25, median, P75, and maximum by treatment group at all scheduled visits.
 
• For the MMRM analyses of change from baseline in PGI-S, an LSMEANS statement will provide adjusted treatment group means and standard errors and a point estimate and two-sided 95% confidence interval for the adjusted mean treatment difference (daprodustat - rhEPO) and a one-sided superiority p-value for this test at Weeks 8, 12, 28, and 52.
 
• Additionally, shift tables by treatment group will be generated that display the number and percentage of subjects in each PGI-S category at baseline and the resulting PGI-S category at each scheduled visit.
 
• Stacked bar charts will be produced by treatment group that display the percentage of subjects with each PGI-S response at baseline and Weeks 8, 12, 28 and 52.
 
• The number and percentage of subjects in each PGI-C category at each scheduled visit will be summarized.
 

Model Results Interpretation

 
• One-sided p-values will be compared to 0.025 to assess nominal significance.
 

Patient Reported Outcomes Statistical Analyses: Symptom Severity & Change
--

- |  |
|--|
| 

• Clinically meaningful effects for PRO assessments will be specified in a separate reimbursement RAP.

 |
|--|

## 10. PHARMACOKINETIC ANALYSES

### 10.1. Secondary Pharmacokinetic Analyses

#### 10.1.1. Endpoint / Variables

- Plasma daprodustat, GSK2391220 (M2), GSK2506104 (M3), GSK2487818 (M4), GSK2506102 (M5), GSK2531398 (M6) and GSK2531401 (M13) PK parameters pre-dose trough (Ctrough) and Cmax

##### 10.1.1.1. Drug Concentration Measures

Refer to [Appendix 5: Data Display Standards & Handling Conventions \(Section 14.5.3 Reporting Standards for Pharmacokinetic\)](#)

##### 10.1.1.2. Derived Pharmacokinetic Parameters

- Pharmacokinetic parameters described in [Table 2](#) will be determined from the plasma concentration-time data, as data permits.

**Table 2** Derived Pharmacokinetic Parameters for daprodustat, and/or GSK2391220 (M2), GSK2506104 (M3), GSK2487818 (M4), GSK2506102 (M5), GSK2531398 (M6) and GSK2531401 (M13)

daprodustat, GSK2391220 (M2), GSK2506104 (M3), GSK2487818 (M4), GSK2506102 (M5), GSK2531398 (M6) and GSK2531401 (M13)	
T max	Time to reach C max , determined directly from the concentration-time data.
C trough	Post-baseline sample pre-dose concentration
C max	Maximum observed concentration of all five post-baseline PK samples, determined directly from the concentration-time data.
Planned Exploratory Displays	

 
Plasma concentration-time data for daprodustat and its six metabolites will be summarized by dose level at the PK sampling using mean, standard deviation, minimum, median and maximum. A listing of Daprodustat and its six metabolites PK plasma concentration-time data will be produced.
 
Plasma PK parameters (Cmax, tmax, and Ctrough) for daprodustat and its six metabolites will be summarized by dose level at the PK sampling using mean, standard deviation, minimum, median, maximum geometric mean, standard deviation of log-transformed data, and %CVb. A listing of PK parameters for daprodustat and its six metabolites will be provided.
 
	

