7.2. Starting Dose and Dose Modification

Participants will be randomized to receive either daprodustat or epoetin alfa.

In order to maintain the treatment blind, each participant will be administered both tablets and IV injections, with one formulation containing active study treatment and the other formulation being an inactive treatment. Refer to Section 7.4 for additional information regarding blinding.

Participants who are randomized to the daprodustat arm will receive the required number of daprodustat tablets to achieve the prescribed dosage of daprodustat based upon the starting dose and dose adjustment algorithms (see Section 7.2.1), and the required number of syringes with saline for IV administration to achieve the prescribed inactive treatment (see Section 7.2.2.2).

Participants who are randomized to the epoetin alfa arm will receive the required number of vials of epoetin alfa to achieve the prescribed dosage of epoetin alfa based upon the starting dose and dose adjustment algorithms (see Section 7.2.2), and the required number of placebo tablets to achieve the prescribed inactive treatment (see Section 7.2.1.2).

The dose of both study treatments will be adjusted, based on the algorithm in Section 7.2.3, in order to maintain Hgb concentrations in the target range. Any required dose adjustments should be started on the day of the study visit at which the dose adjustment was prescribed. In circumstances where a new supply of study treatment (including a new dose) cannot be dispensed on the day of the study visit, the new supply of study treatment can be dispensed at the next dialysis session, and the prior study treatment should be continued unless on a dose interruption.

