9.5.1. PK Visit

On the day of the scheduled (post-baseline) PK visit:

- The participant will take the required dose of study treatment tablets in the clinic after the pre-dose sample is collected.
- The participant must not be on a dose interruption or be receiving a dose of 0 mg (tablets). If the participant's study treatment is interrupted or decreased to a 0 mg on the day of the planned PK visit, then the PK samples should be collected at the next possible study visit up to Week 52, inclusive.
- Record the date and actual time that the study treatment tablets were taken in the clinic, and the date and actual time of all PK samples collected. Samples may be collected within ± 20 minutes of the planned collection time.
- Based on the time of dosing, samples may be obtained before, during, or after any dialysis procedure. The start and stop time of the dialysis procedure will also be recorded at this visit.

Plasma PK analysis will be performed under the control of GSK PTS-IVIVT-BIB, the details of which will be included in the SRM. Concentrations of parent daprodustat and metabolites (GSK2391220 [M2], GSK2506104 [M3], GSK2487818 [M4], GSK2506102 [M5], GSK2531398 [M6], and GSK2531401 [M13]) will be determined in plasma samples using the currently approved bioanalytical methods. Raw data will be archived at the bioanalytical site.

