10.3.3.2. Pharmacokinetic/Pharmacodynamic Analyses

The following plasma PK parameters will be determined for daprodustat and its predominant metabolites: C_{tau} (pre-dose) and C_{max}.

Plasma daprodustat and metabolite concentration data will be listed and summarized by planned collection time and daprodustat dose administered at the PK visit. PK parameter data will be listed and summarized by daprodustat dose administered at PK visit, and dose-normalized (per mg) PK parameter data will also be summarized.

The exploratory graphics described below will be created. Based on these, and the efficacy and safety results obtained, post-hoc exploratory exposure-response/safety modeling may be conducted.

- Scatter plots of C_{max} of three-times weekly dosed daprodustat extrapolated to daprodustat dose at the PK sample multiplied by the mean weekly daprodustat dose during the EP vs. the percent time within the Hgb target range during the EP
- Scatter plots of C_{max} of three-times weekly dosed daprodustat extrapolated to daprodustat dose at the PK sample multiplied by the mean weekly daprodustat dose over 52 weeks vs. mean Hgb over the 52-week treatment period

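### Ctrough is summarised under the dose given at the PK visit, which is the wrong dose for participants who start a different non-zero dose that day

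*SAP*

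**What the plan says.** Ctrough and Cmax of daprodustat and six metabolites are secondary endpoints (protocol section 4). They are analysed under the SAP 10.1 heading "Secondary Pharmacokinetic Analyses". SAP 10.1.1.2 and 14.6.5 define Ctrough as "Post-baseline sample pre-dose concentration".

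One dose label serves every parameter, for the parent drug as for the rest (SAP 10.1.1.2): "its six metabolites will be summarized by dose level at the PK sampling using mean, standard deviation, minimum, median, maximum geometric mean". The concentration-time data carry the same label, so it also covers the pre-dose row of Table 5.001. Protocol 10.3.3.2 settles which dose is meant: "PK parameter data will be listed and summarized by daprodustat dose administered at PK visit". It also plans per-mg versions.

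The order of events on the day comes from two protocol sections:

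- Section 9.5.1: "The participant will take the required dose of study treatment tablets in the clinic after the pre-dose sample is collected".
- Section 7.2: "Any required dose adjustments should be started on the day of the study visit at which the dose adjustment was prescribed". If new supply cannot be dispensed that day, "the new supply of study treatment can be dispensed at the next dialysis session, and the prior study treatment should be continued" (unless the dose is interrupted).

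The only restriction on dose status at the PK visit is in section 9.5.1: "The participant must not be on a dose interruption or be receiving a dose of 0 mg (tablets". The PK visit may be any one visit from Week 8 to Week 52, preferably early (section 9.5).

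**The concern.** The pre-dose sample can reflect only earlier dosing, while the label is the dose taken afterwards. The two agree when the dose is unchanged and part when a new dose starts at that visit. Each scheduled visit in the PK window is also one at which the dose algorithm runs (protocol 7.2.3). Early sampling is preferred, and protocol 5.5 expects individual dose adjustments in the first months of treatment, so some PK visits will probably coincide with a change.

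At stake is how trough by dose level reads for the three-times-weekly regimen. Some values in a dose row would come from the step above or below. That can shift the row's mean and tends to widen its SD and %CVb, both of which the SAP reports.

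**Working it through.** The documents give no figure to reproduce. The check has three parts.

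**1. Sequence.** Take a participant on 12 mg who is assigned 16 mg at the PK visit and has supply that day.

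- Pre-dose sample: follows 12 mg. This is Ctrough.
- Tablets: 16 mg.
- Samples at 0.5, 1, 2 and 3 hours: follow 16 mg. Cmax normally comes from these.
- Label on both parameters: 16 mg.

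The label fits Cmax and does not fit Ctrough. Protocol 9.5.1 defers sampling only for an interruption or a 0 mg dose, so this participant is sampled. SAP 14.5.3 and 14.6.5 contain no rule that relabels or sets aside the trough. If supply comes at the next session instead, the visit dose is still 12 mg and the label is right.

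**2. Size per affected participant.** The dose levels are 2, 4, 8, 12, 16, 20, 24, 32 and 48 mg (protocol Tables 3 and 5), and changes are one step at a time. Ratio = dose before the sample / dose on the label.

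| Increase (mg) | Ratio | Decrease (mg) | Ratio |
|---|---|---|---|
| 2 to 4 | 2/4 = 0.50 | 4 to 2 | 4/2 = 2.00 |
| 4 to 8 | 4/8 = 0.50 | 8 to 4 | 8/4 = 2.00 |
| 8 to 12 | 8/12 = 0.67 | 12 to 8 | 12/8 = 1.50 |
| 12 to 16 | 12/16 = 0.75 | 16 to 12 | 16/12 = 1.33 |
| 16 to 20 | 16/20 = 0.80 | 20 to 16 | 20/16 = 1.25 |
| 20 to 24 | 20/24 = 0.83 | 24 to 20 | 24/20 = 1.20 |
| 24 to 32 | 24/32 = 0.75 | 32 to 24 | 32/24 = 1.33 |
| 32 to 48 | 32/48 = 0.67 | 48 to 32 | 48/32 = 1.50 |

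The range is 0.50 to 0.83 after an increase and 1.20 to 2.00 after a decrease. Starting doses lie between 8 and 24 mg. One-step increases from levels in that span give 0.67 to 0.83. The extremes of 0.50 and 2.00 arise only among 2, 4 and 8 mg.

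**3. Illustration for a dose-level mean.** This needs two assumptions that the documents do not supply: a share *f* of values in the row from same-day changes, and trough proportional to dose. With ratio *r* from the table:

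recorded mean / mean at the labelled dose = (1 − *f*) + *f* × *r*

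Example: *f* = 0.10 at 20 mg, all increases from 16 mg, gives 0.90 + 0.10 × 0.80 = 0.98. Over the levels 4 to 32 mg:

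| Assumed *f* | All increases | All decreases | Even mix |
|---|---|---|---|
| 10% | 0.950 to 0.983 | 1.020 to 1.100 | 1.000 to 1.025 |
| 30% | 0.850 to 0.950 | 1.060 to 1.300 | 1.000 to 1.075 |

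An even mix moves the mean little, because errors in the two directions partly cancel. It does not remove the extra spread.

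**The case against.** The strongest reply is that this is a labelling detail in a descriptive table. Much of that stands. Ctrough is not tested. The SAP puts this summary under planned exploratory displays, and its exposure-efficacy and exposure-safety displays (7.4.1, 8.2) use Cmax or dose. Individual concentrations, parameters and exposure records are listed, so an analyst could recover the right dose. The algorithm keeps the dose unchanged for most Hgb values between 9.5 and 11.5 g/dL, and late supply keeps the label correct, so the affected share may be small. Display standards and a study manual that are not available here could add a rule.

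A reader might also infer more than the documents support:

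- **That troughs after a hold are mixed in as near-zero values.** Section 9.5.1 says the participant must not be on an interruption, and someone restarting that day is arguably still on hold when the pre-dose sample is drawn. Its next sentence, on deferral, mentions only treatment interrupted or cut to 0 mg that day. This is an ambiguity, not a demonstrated error.
- **That the dose ratios are errors in the measured trough.** Neither document states that trough is proportional to dose. Protocol 9.3 ties monitoring after an overdose to drug no longer being detectable, at least 2 days. PK visits on a three-times-weekly schedule avoid the session after the longest gap, so the pre-dose sample falls about 2 days after the last dose. Parent drug may be low by then at any dose. That is an inference, and it does not settle the metabolites.
- **That per-mg troughs in the SAP are wrong.** Dose-normalised Ctrough appears only in the protocol; the SAP lists only Cmax per 1 mg.
- **That the same-dose rule for two-day PD sampling shows an inconsistency.** That rule exists because one post-dose profile is split over two days, and SAP 11.1 likewise summarises PD values by the PD visit dose.
- **That this study is the only source of PK for the regimen.** Protocol section 11 cites an earlier 29-day three-times-weekly study that also evaluated PK.

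None of this makes the label right for a same-day change between two non-zero doses.

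**Conclusion.** The point holds for a subset: participants who start a different non-zero dose on the PK visit day. For them Ctrough, and the pre-dose row of the concentration table, is filed under a dose not yet taken. The dose ratios follow from the dose steps alone. The size of that subset is unknown, and the effect on means rests on the two assumptions stated with the illustration. It would be wrong to conclude that the secondary PK endpoint as a whole is assigned to the wrong dose: unchanged-dose visits are labelled correctly, Cmax normally follows the visit dose, and the primary and principal secondary analyses do not use PK. The change is worth making before unblinding because a stated rule mislabels a secondary endpoint and the data to correct it are already collected.

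**What to change.** In SAP 10.1.1.2, 14.6.5 and Tables 5.001 and 5.002:

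- Summarise Ctrough and the pre-dose concentration, and any dose-normalised Ctrough, by the last active daprodustat dose actually taken before the pre-dose sample. Use the dosing dates and times that protocol 7.6 requires in the eCRF. SAP 14.6.3.5 already derives a most recent dose before a scheduled visit, which can serve as a cross-check.
- Flag and count participants whose dose changed on the PK day.
- Flag and count participants with no active dose in the preceding dosing interval, and leave them out of the dose-level trough summary. The SAP must state that interval, as the documents give no cut-off.
- Keep Cmax and tmax by the visit dose, and footnote that the tables use two dose labels.

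The two sentences in protocol 9.5.1 on interruption also need reconciling, so that it is clear whether a participant restarting that day may be sampled.

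The cost is a wording and programming change, a footnote, and two dose labels for some participants within one table. A few values may leave the dose-level trough summary. No new data or study procedure is needed.
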